Unique Protocol ID: No.2023023

Official Title: Effects of transcranial direct current stimulation combined with retrieval practice on semantic memory in patients with schizophrenia

Document Title: Study Protocol

Date of the Document: 2024/7/31

Study Protocol

Effects of transcranial direct current stimulation combined with retrieval practice on semantic memory in patients with schizophrenia

1. Introduction

Research on semantic memory in schizophrenia patients has revealed weaker activation in the prefrontal cortex, potentially linked to cognitive impairments [1,2]. Prior studies have suggested that continuous periodic tDCS intervention in the left dorsolateral prefrontal cortex (L-DLPFC) can enhance semantic recognition abilities [3]. Semantic memory organization in schizophrenia patients approaches that of healthy individuals after undergoing continuous tDCS stimulation of the left DLPFC for five days, ten times [4]. Thus, stimulating the excitability of the L-DLPFC through tDCS can effectively ameliorate semantic memory impairments in schizophrenia patients and is the preferred area for interventions in semantic memory treatment.

As an effective learning strategy, retrieval practice can assist patients in enhancing semantic elaboration and boosting memory performance [5]. Research utilizing near-infrared brain imaging technology to observe brain regions during retrieval practice has revealed that during challenging word retrieval tasks, activation levels in the inferior frontal gyrus, Frontal polar region, and dorsolateral prefrontal cortex area are significantly higher compared to conditions without retrieval, aligning closely with the regions activated by tDCS [6]. This

suggests that there is consistency in brain activation between tDCS and retrieval practice, and combining the two may result in mutually reinforcing effects.

A study involving 119 healthy subjects investigated the combination of tDCS intervention with retrieval practice and found that the strong retrieval practice effect left no room for tDCS to improve memory performance[7]. The combination of single-session online tDCS with retrieval practice in healthy individuals and found that the memory performance of anodal stimulation was inferior to cathodal stimulation and sham stimulation [8]. We have already explored the role of continuous periodic tDCS combined with interim testing on spatial route learning in patients with schizophrenia in a previous study [9], and found that both the learning strategy and tDCS independently facilitated the ability of patients with schizophrenia to learn new information in spatial route learning, suggesting that the tDCS of L-DLPFC has a significant improvement effect. In contrast, targeted tDCS treatment may be more effective for memory-impaired populations such as schizophrenia [10]. Therefore, further investigation is needed to determine the effectiveness of combining tDCS and retrieval practice for semantic memory intervention in schizophrenia patients. From a theoretical perspective, this combination may have a dual activation effect because (1) tDCS stimulation can enhance activation levels of the L-DLPFC, improving its cognitive function impairment; (2) retrieval practice can not only help patients initiate semantic memory strategies and promote semantic elaboration but also actively activate the brain regions stimulated by tDCS, thereby producing a synergistic effect.

Therefore, this study aims to investigate whether combining tDCS with retrieval practice facilitates the maintenance of semantic memory and improvement of semantic organization by comparing the use of retrieval practice strategies in patients receiving anodal L-DLPFC stimulation, sham stimulation.

2. Methods

2.1 Participants

55 schizophrenic patients expected to be recruited from the mental health center. All patients must sign an informed consent form.

Patients with schizophrenia were diagnosed and assessed by two chief psychiatrists. Neuropsychological background tests included the Montreal Cognitive Assessment (MoCA)[11] for general cognitive function and the Positive and Negative Syndrome Scale (PANSS)[12]. A parallel-group, single-blind study design was used to assign subjects to the two stimulus types using a stratified randomization method based on baseline Montreal Cognitive Assessment performance. The characteristics of the participants are presented in Table 1, showing no significant differences in participant characteristics between the two stimulation types groups.

Patients with schizophrenia were included based on the following criteria: (1) meeting the diagnostic criteria for schizophrenia according to the Diagnostic and Statistical Manual of Mental Disorders, Fifth Edition (DSM-5); (2) aged 18 years or older, regardless of gender, with an educational level of elementary school or above; (3) all patients received stable-level

antipsychotic medication treatment, were in a stable phase of disease treatment, able to understand the testing requirements, and cooperated to complete all research tasks; (4) no history of neurological disorders or other serious physical illnesses, and no history of intellectual disability; (5) no color blindness, color weakness, or other color vision impairments, with normal vision or corrected vision.

Exclusion criteria were as follows: (1) clear cognitive impairment caused by somatic or cerebral organic lesions, such as cerebrovascular diseases, traumatic brain injury, etc; (2) individuals with mental disorders caused by substance dependence or abuse, or the use of psychoactive substances; (3) history of brain injury or other central nervous system-related organic diseases; (4) individuals at significant risk of suicide or harming others; (5) participation in similar experiments in the past 30 days prior to baseline.

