2.2 Design

A mixed experimental design of 2 (Stimulation type: anodal stimulation, sham stimulation) \times 2 (Learning strategy: retrieval practice, restudy) \times 2 (Retention interval: Immediate recall, Delayed recall) was employed. Stimulation type was a between-subjects variable, while learning strategy and testing time were within-subject variables. The dependent variables were the correct recall rate and Adjusted Ratio of Clustering (ARC) scores in the testing phase.

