2.4 Procedure

Treatment was administered by two examiners, and after a total of 10 sessions over 5 consecutive days, a final group of 52 patients participated in the learning and testing phase. Among them, 27 received anodal stimulation, while 25 received sham stimulation. Each participant of each stimulation type was involved in both learning conditions, meaning that all participants completed both retrieval and restudy learning and testing (experimental procedure in **Figure 1**).

(1) Stimulation phase

In the anodal group, the anode was placed over the left DLPFC (F3), and the cathode was placed over the contralateral supraorbital area (FP2). A direct current of 2mA was applied for 20 minutes during each stimulation session. Stimulation was conducted twice a day, at 9 a.m. and 2 p.m., for 5 consecutive days, totaling 10 sessions. In the sham group, the stimulation parameters, including the stimulation site and duration, were identical to those of the anodal group. However, during the 10-second ramp-up and ramp-down periods before and after stimulation, patients were unaware that the current was turned off.

(2) Learning phase

The experimental procedure followed the classic retrieval practice paradigm, which included a learning phase and a final test phase.

During the experiment, participants were informed that they would learn two lists of words. Subsequently, they might either learn the words again or complete a list recall test, and will be given a final test shortly thereafter. The learning of the retrieval practice list and the restudy list was conducted in a randomly balanced manner. Each word was presented for 5 seconds, with a 500-millisecond interval between words. To avoid providing secondary retrieval cues between examples, all words were shuffled pseudo-randomly within categories. Each list contained 17 words, consisting of 5 examples from each of the 3 experimental categories (15 experimental examples, 2 filler examples). The first and last words presented in each list were filler words, thus controlling for the primacy and recency effects on memory.

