2.5 Date scoring & analysis

The experimental results were processed using SPSS 26.0. The correct recall rate of word lists was calculated for each subject by the experimental assistant. Then, Free recall organization was measured by the Adjusted Ratio of Clustering (ARC) scores [14,15]. ARC scores range from 1 to 1. A 0 score indicates a level of clustering similar to what would be expected by chance, and a score of 1 implies perfect clustering. Negative values of ARC scores mean atypical and uninterpretable recall patterns[16]. For that reason, negative scores were excluded from analyses.

A mixed-design analysis of variance (ANOVA) was conducted to compare the correct recall rates and ARC clustering scores between the two learning strategies under two stimulation conditions. All statistical tests were performed at a significance level of 0.05, and post-hoc comparisons were adjusted using Bonferroni correction. Effect sizes were reported using partial eta-squared (η_p^2 ; ANOVAs).

3. Study Status

Record Verification: July 2024

Overall Status: Completed

Study Start: July 24, 2023 [Actual]

Primary Completion: January 30, 2024 [Actual]

Study Completion: April 15, 2024 [Actual]

List of abbreviations

tDCS transcranial direct current stimulation

L-DLPFC left dorsolateral prefrontal cortex

VLPFC ventrolateral prefrontal cortex

ARC Adjusted Ratio of Clustering

References

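### Allocation is stratified on baseline MoCA but the stated mixed ANOVA omits it, so anodal-versus-sham comparisons lose precision if MoCA predicts the outcome

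*Protocol*

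**What the plan says.** - **Allocation (Protocol 2.1).** Patients are assigned to the two stimulation types "using a stratified randomization method based on baseline Montreal Cognitive Assessment performance". MoCA is described there as the measure of general cognitive function and is the only stratifier named. The cut-points, number of strata and block size are not given.
- **Design (2.2).** "Stimulation type was a between-subjects variable, while learning strategy and testing time were within-subject variables". On outcomes: "The dependent variables were the correct recall rate and Adjusted Ratio of Clustering (ARC) scores in the testing phase".
- **Analysis (2.5).** "A mixed-design analysis of variance (ANOVA) was conducted to compare the correct recall rates and ARC clustering scores between the two learning strategies", under the two stimulation conditions. The level is 0.05, "post-hoc comparisons were adjusted using Bonferroni correction", and effect size is partial eta-squared. No covariate or stratum term is named.
- **Numbers (2.4).** Of the 52 patients in the learning and testing phase, "27 received anodal stimulation, while 25 received sham stimulation".
- **Aim (section 1).** To find out "whether combining tDCS with retrieval practice facilitates the maintenance of semantic memory", by comparing retrieval practice under anodal and sham stimulation.
- **Status (section 3).** "Overall Status: Completed".

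**The concern.** The design singles out baseline MoCA as the patient characteristic worth controlling at allocation, and the analysis then does not use it. The outcomes are word recall and its semantic clustering, so a measure of general cognition may well be prognostic for them.

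Stimulation is the only between-subject factor, and its main effect is tested against variation between 52 patients. Any part of that variation explained by MoCA is left in the error term. The same holds for comparing anodal with sham within one strategy or at one interval, which the Bonferroni post-hoc tests may include.

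Two effects are possible:

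1. **Lost precision.** This follows whenever MoCA is prognostic, however the allocation was done.
2. **A conservative test.** If the arms were also balanced within MoCA strata, the unadjusted standard error is larger than the true sampling variation, and the real type I error falls below 5%.

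At stake is a real anodal effect being missed, or estimated with a wider interval than necessary.

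**Working it through.** The protocol gives no power, effect size or standard deviation, so there is no planned figure to reproduce.

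**Inputs from the protocol.** 27 anodal and 25 sham (27 + 25 = 52); significance level 0.05.

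**Assumptions, not in the protocol.** Two-sided tests before any Bonferroni step; correlation r between MoCA and a patient's mean outcome from 0 to 0.6; standardised difference d = 0.7; correlation 0.6 between a patient's four strategy-by-interval cells; all 52 patients contribute. ARC may have fewer, because 2.5 excludes negative scores.

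**Step 1: analytic size, stimulation main effect.** In outcome SD units the unadjusted standard error is √(1/27 + 1/25) = 0.278, so the noncentrality is 0.7/0.278 = 2.52 on 50 df. Adjusting for MoCA multiplies the standard error by √(1 − r²) and leaves 49 df. The equivalent sample size is 52/(1 − r²). This is slightly optimistic, because it ignores the lost degree of freedom and chance imbalance in MoCA.

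| r | SE multiplier | Equivalent n | Power, d = 0.7 | Smallest d with 80% power |
|---|---|---|---|---|
| unadjusted | 1 | 52 | 69.6% | 0.79 |
| 0.2 | 0.98 | 54 | 71.3% | 0.78 |
| 0.3 | 0.95 | 57 | 73.6% | 0.76 |
| 0.5 | 0.87 | 69 | 81.5% | 0.69 |
| 0.6 | 0.80 | 81 | 87.1% | 0.635 |

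At d = 0.5, power is 42% unadjusted, against 46%, 53% and 60% at r = 0.3, 0.5 and 0.6.

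**Step 2: simulation, stimulation main effect.** 20,000 runs per setting, n = 52. Allocation was either by permuted blocks of 4 within two or three equal MoCA strata, or by simple randomisation with no balance within strata. Entries are percentages; blocked ranges cover two and three strata.

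| r | Unadjusted type I error, blocked | Same, simple | Power without → with MoCA, blocked | Same, simple |
|---|---|---|---|---|
| 0 | 4.9 | 4.9 | 69.4–69.8 → 69.1–69.4 | 68.7 → 67.7 |
| 0.2 | 4.6–4.8 | 5.0 | 70.1–70.2 → 71.4–71.5 | 68.7 → 69.2 |
| 0.3 | 4.3–4.5 | 5.0 | 69.5–70.2 → 72.6–73.3 | 68.7 → 71.8 |
| 0.5 | 3.0–3.4 | 4.9 | 70.9–71.1 → 81.2–81.4 | 69.0 → 80.1 |
| 0.6 | 2.2–2.6 | 4.8 | 71.5–72.9 → 86.9–87.0 | 68.2 → 85.4 |

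The MoCA-adjusted type I error was 4.8–5.3% throughout. A separate simulation with exact balance within a median split shows the mechanism at r = 0.5: the unadjusted model reports a mean standard error of 0.276, while the estimate's true sampling SD is 0.253. Its type I error is 3.0%.

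**Step 3: anodal versus sham within part of the data.** With cell correlation 0.6, the variance is (1 + 3 × 0.6)/4 = 0.7 for a mean of four cells, (1 + 0.6)/2 = 0.8 for a mean of two, and 1 for one cell. A correlation of 0.5 with the patient mean is therefore 0.5 × √(0.7/0.8) = 0.47 within one strategy and 0.5 × √0.7 = 0.42 within one cell, so the gain shrinks but remains. Simulated power under blocking at r = 0.5 goes from about 71% to 79–80% within one strategy, and from 70–71% to 77–78% within one cell.

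**Step 4: the interactions.** Stimulation × strategy compares the arms on each patient's retrieval-minus-restudy difference. An additive MoCA effect is the same in both terms and cancels. In simulation the type I error is 4.7–5.3% with or without MoCA. Adding it lowers power by 0.1–0.6 point (blocked) or 0.9–1.2 points (simple). Stimulation × interval behaves identically under the assumed cell structure.

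**The case against.** **The matter could belong to an analysis plan that is not at hand.** Adjustment for stratifiers is often settled there, and 2.5 does not exclude MoCA. The ANOVA sentence also does not list every term; the factors have to be read with 2.2. This carries some weight, but the protocol does not defer the model. It names the design, factors, test, level, post-hoc correction and effect size, and says in the past tense what was done. A later plan could add MoCA; the model as stated lacks it.

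**Nothing is invalid, and the main question is about synergy.** Both parts stand. The unadjusted comparison is unbiased, and the interactions do not benefit. But the stimulation main effect is a direct output of the stated ANOVA. The aim can also be read as anodal versus sham within retrieval practice, which carries between-patient variance.

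**The size is assumed.** This stands. At r = 0.2 the gain is only 0.5 to 1.7 points, depending on the calculation, and at r = 0 there is a small loss. The conservatism needs balance within strata, which the protocol does not state.

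**Continuous MoCA goes beyond respecting the stratification.** Partly true. With exact balance within a median split, d = 0.6 and r = 0.5, power is 57.6% unadjusted, 64.3% with the stratum and 68.6% with continuous MoCA. So 6.7 of the 11 points come from the stratum itself. Since the cut-points are not given, the continuous score is the version that can be specified from the protocol.

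**The study is complete.** This stands and limits the remedy to a supporting analysis.

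**Conclusion.** The concern holds as an efficiency point. The protocol stratifies on baseline MoCA and states an analysis without it. If MoCA is prognostic, anodal-versus-sham comparisons that carry between-patient variance are less precise than they need be. For the main effect at d = 0.7, the power forgone is roughly 3–4 points at r = 0.3, 10–12 at r = 0.5 and 14–17 at r = 0.6; it is negligible at r of 0.2 or less. If allocation was balanced within strata, the unadjusted test is also conservative, with a real level of about 3.0–3.4% at r = 0.5. Without that balance it stays near 5% and only the precision loss remains.

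There is no bias and no inflation of false positives, and conclusions drawn from the interactions are unaffected unless MoCA modifies the strategy or interval effect. The direction is secure; the size rests on the assumed r. The change should be made, but the stated analysis is not unsound without it.

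**What to change.** Keep the ANOVA stated in 2.5 as the governing analysis. Add one sentence there: for recall and for ARC, the same model is also reported with mean-centred baseline MoCA as a between-subject covariate, because allocation was stratified on it, and this analysis was added after completion. Show the anodal-versus-sham estimates and intervals from both models side by side. Take the stimulation × strategy and stimulation × interval conclusions from the stated ANOVA, and do not present the adjustment as improving them.

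The cost is one sentence, one covariate already collected and one between-subject error degree of freedom (50 to 49). If MoCA proves unrelated to the outcome, the adjusted main-effect test loses 0.3–0.4 point of power under blocked allocation, or about 1 point without balance within strata.

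### Non-significant baseline tests do not show that the arms are balanced, and the stated ANOVA adjusts for neither MoCA nor PANSS; the cost is conditional bias and lost precision in the anodal-sham comparison

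*Protocol*

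**What the plan says.** Protocol section 2.1 names MoCA and PANSS as neuropsychological background tests. It assigns patients to the two stimulation types "using a stratified randomization method based on baseline Montreal Cognitive Assessment performance", so MoCA is the only stratification factor. It then describes the arms by reference to Table 1, "showing no significant differences in participant characteristics between the two stimulation types groups". Table 1 itself is not in the text available.

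Section 2.2 fixes three factors: "Stimulation type was a between-subjects variable, while learning strategy and testing time were within-subject variables". Section 2.5 specifies a mixed-design ANOVA for recall and ARC scores with Bonferroni-adjusted post-hoc comparisons, and states that "All statistical tests were performed at a significance level of 0.05". Neither section names a covariate.

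Section 2.4 gives the numbers who reached learning and testing: "Among them, 27 received anodal stimulation, while 25 received sham stimulation". It places learning and testing after the ten stimulation sessions and describes no recall score taken before stimulation.

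**The concern.** A non-significant baseline test is not evidence that two arms are alike. In a trial of this size it mostly reflects low power, and it does not address whether an imbalance matters for recall. A reader told that no difference was significant may take balance as shown.

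This matters because stimulation is the only between-patient factor and there is no pre-stimulation recall or ARC score to absorb prior differences. Any chance difference between the arms in a characteristic related to recall passes, in proportion to that relation, into the stimulation main effect and into each anodal-sham comparison within a strategy. PANSS is the clearest case: it is collected, but it is neither a stratification factor nor in the stated model. MoCA is balanced by design, yet it is also left out of the model, so whatever it explains of the between-patient variance stays in the error term.

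**Working it through.** The protocol gives no sample-size, power or detectable-difference figure, so there is none of its own to reproduce.

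**Inputs.** Arms of 27 and 25 (section 2.4). Alpha 0.05 (section 2.5), taken as two-sided because sidedness is not stated. The correlation r between a covariate and recall is not in the documents; a range of 0.1 to 0.5 is assumed.

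**1. Largest difference that still passes as non-significant** (two-sample t-test, in SD units of the baseline variable):

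- Standard error = sqrt(1/27 + 1/25) = 0.2776
- Critical t with 50 degrees of freedom = 2.0086
- Ceiling = 2.0086 × 0.2776 = **0.557 SD**

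If the 55 patients of the recruitment target were split 28 and 27, the ceiling would be 0.541 SD.

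**2. Power of the baseline test** (non-central t, 50 degrees of freedom): 19% for a true difference of 0.3 SD, 29% for 0.4 SD and 42% for 0.5 SD.

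**3. Imbalance to expect by chance in an unstratified variable.** The standardised difference has SD 0.2776. Its mean absolute size is 0.2776 × sqrt(2/π) = 0.2776 × 0.798 = **0.22 SD**. It exceeds 0.3 SD about 28% of the time and 0.5 SD about 7% of the time. These figures suit PANSS; for MoCA the stratification should make the imbalance smaller.

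**4. Consequence for the anodal-sham comparison.** Shift = r × imbalance, in outcome SD. The type I error conditional on a 0.557 SD imbalance uses a normal approximation: the unadjusted test statistic then has mean r × 2.0086 and SD sqrt(1 − r²), and is compared with ±1.96. The gain in effective sample size from adjustment is 1/(1 − r²) − 1.

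| r (assumed) | Shift at 0.22 SD | Shift at 0.557 SD | Conditional type I error at 0.557 SD | Gain in effective n |
|---|---|---|---|---|
| 0.1 | 0.02 | 0.06 | 5.3% | 1% |
| 0.2 | 0.04 | 0.11 | 6.4% | 4% |
| 0.3 | 0.07 | 0.17 | 8.1% | 10% |
| 0.4 | 0.09 | 0.22 | 10.5% | 19% |
| 0.5 | 0.11 | 0.28 | 13.5% | 33% |

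**5. Cost of adjustment.** Each covariate takes one of 50 error degrees of freedom, about 1/50 = 2%. Setting 1/(1 − r²) − 1 = 0.02 gives r² = 0.0196, so the break-even correlation is about r = 0.14.

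**6. Which effects are touched.** If a covariate adds the same amount to a patient's recall under both strategies and at both intervals, it cancels from every within-patient difference. It therefore drops out of the strategy effect and of the stimulation × strategy interaction. It stays in the stimulation main effect and in the anodal-sham comparison within either strategy.

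**The case against.** The case on the other side is substantial, and much of it stands.

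- *Nothing in the analysis depends on the baseline tests.* This stands. The sentence in section 2.1 is descriptive: no covariate is chosen and no model changed because of it. A reader might infer that the baseline tests act as a decision rule, but section 2.5 contains none.
- *No imbalance is known.* This stands. A reader might infer that the arms differ by about 0.56 SD. That figure is only the most that could go unflagged, and chance alone produces a difference that large about 5% of the time. Table 1 may already show means and SDs.
- *Randomisation protects the test.* This stands. The unadjusted ANOVA keeps its overall 5% error rate, and its standard error already allows for chance imbalance. PANSS is balanced in expectation, and MoCA stratification helps as far as the two correlate. The inflated error rates above are conditional on an extreme imbalance, not properties of the plan overall.
- *The aim concerns combining stimulation with retrieval practice, that is, the interaction.* This stands for additive covariate effects. The protocol nevertheless also compares the arms directly through the stimulation factor, and those comparisons are exposed.
- *PANSS may not have been measured before stimulation.* This stands as a caveat. The text attaches the word baseline to MoCA only.
- *Covariates belong in the SAP, which is not shown.* This stands in part. An SAP might name them, so their absence here does not prove that no adjustment was planned. But the protocol states a model and that model is unadjusted; an SAP that added covariates would depart from it. The comparability statement is the protocol's own.

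**Conclusion.** The point holds in limited form. The non-significance statement does not show that the arms are balanced, because differences up to 0.557 SD pass and power is 42% or less for true differences up to 0.5 SD. The stated model also leaves out two measures the trial already collects. The cost is conditional bias and lost precision in the between-arm comparisons; the documents do not support a claim of inflated overall type I error, of a demonstrated imbalance, or of bias in the stimulation × strategy interaction under additive effects.

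The likely size is modest: a shift of 0.02 to 0.11 SD at a typical imbalance, with 0.06 to 0.28 SD as the range at the ceiling. The precision gain runs from about 1% more patients, which does not repay the lost degree of freedom, to 33%, which would be appreciable in a trial of 52. All of these rest on the assumed correlation of 0.1 to 0.5, on two-sided testing, and, for PANSS, on measurement before stimulation. The improvement is worth making; the unadjusted analysis is not invalid without it.

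**What to change.** 1. In section 2.1, drop the non-significance statement as evidence of comparability. Report means, SDs and standardised differences by arm.
2. Confirm and state that PANSS was measured before stimulation.
3. In section 2.5, add MoCA and pre-stimulation PANSS total as covariates in the mixed model, whatever Table 1 shows. If the stimulation × strategy term is also meant to benefit, add the covariate × strategy terms.
4. Section 3 gives study completion as April 2024 and the document is dated 31 July 2024. Label the adjusted analysis post hoc, beside the unadjusted one, unless it was documented before the data were seen.

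The cost is a few sentences and one re-run of the model, with no new data. Two covariates use two of 50 error degrees of freedom, about 4%.

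### Does inclusion criterion (3) restrict the anodal–sham comparison to patients who completed every task?

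*Protocol*

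**What the plan says.** Protocol Section 2.1 introduces its eligibility list with "Patients with schizophrenia were included based on the following criteria". Item (3) covers stable medication and stable illness, and ends by requiring that patients be "able to understand the testing requirements, and cooperated to complete all research tasks". The same section gives a recruitment target, "55 schizophrenic patients expected to be recruited from the mental health center", and says the design was used to "assign subjects to the two stimulus types using a stratified randomization method based on baseline Montreal Cognitive Assessment performance". It gives no number randomised, in total or by arm. It also cites a Table 1 of participant characteristics, which is not in the text at hand.

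Section 2.4 counts patients once, after the ten stimulation sessions: "a final group of 52 patients participated in the learning and testing phase". It continues: "Among them, 27 received anodal stimulation, while 25 received sham stimulation". It then explains that each patient took part in both learning conditions, "meaning that all participants completed both retrieval and restudy learning and testing".

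Section 2.5 states the analysis: "A mixed-design analysis of variance (ANOVA) was conducted to compare the correct recall rates and ARC clustering scores".

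**The concern.** An entry condition has to be something that can be judged before allocation. Stimulation, learning, the immediate test and the 24-hour test all come after it. Taken at its word, criterion (3) would let a randomised patient who stopped partway be reclassified as ineligible and dropped.

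Two other places seem to fit that reading. Arm sizes are stated only for the group left after treatment. The planned ANOVA, with strategy and interval both within patient, in its standard form uses only patients with all four recall cells.

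If patients had been dropped this way, and if dropping out were related to both arm and cognition, randomisation would no longer protect the anodal–sham difference. The sponsor stratified on baseline MoCA and so treats cognition as relevant to outcome. That makes the worry reasonable.

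**Working it through.** **Reading the text**

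- *Tense.* The document is dated 31 July 2024 and Section 3 gives study completion as 15 April 2024. Most of the methods are reported in the past tense, and so is criterion (3), where patients received medication and were stable. A past-tense verb here is the document's style and does not point to a filter applied after allocation.
- *Grammar.* Cooperation is joined to being able to understand the tests, which is a baseline capacity. Ability to cooperate is the natural sense.
- *Section 2.4.* The sentence that all participants completed both conditions explains the within-patient factor of Section 2.2. It does not describe how patients were selected.
- *Section 2.5.* A mixed ANOVA is the ordinary analysis for this design under either reading of the criterion.

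**Counts**

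27 + 25 = 52, as stated. Against the target, 55 − 52 = 3, or 3/55 = 5.5%. The 55 is an expected figure, so the 3 need not be losses after randomisation.

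**Size if there were three such losses**

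From the document: 27, 25 and the 5% level (two-sided assumed). Assumed: 3 losses after randomisation; lost patients 0.2–0.3 lower in recall rate than completers; SD 0.2 per recall cell; correlation 0.5 between a patient's cells.

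- Shift in the arm difference = [a/(27+a) − s/(25+s)] × deficit, with a and s lost from anodal and sham.
- SE = SD × √(1/27 + 1/25) = SD × 0.2776.
- Type I error = Φ(−1.96+b) + Φ(−1.96−b), where b = |shift|/SE.

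For a single recall cell, SD 0.2 gives SE 0.0555. The ANOVA main effect of stimulation averages four cells, so its SD is 0.2 × √[(1+3×0.5)/4] = 0.158 and its SE is 0.0439. Both are shown.

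| Lost (anodal, sham) | Multiplier | Absolute shift | b, single cell | Type I error | b, four-cell mean | Type I error |
|---|---|---|---|---|---|---|
| 3, 0 | 0.1000 | 0.020–0.030 | 0.36–0.54 | 6.5–8.4% | 0.46–0.68 | 7.4–10.5% |
| 0, 3 | −0.1071 | 0.021–0.032 | 0.39–0.58 | 6.7–8.9% | 0.49–0.73 | 7.8–11.3% |
| 2, 1 | 0.0305 | 0.006–0.009 | 0.11–0.17 | 5.1–5.3% | 0.14–0.21 | 5.2–5.5% |
| 1, 2 | −0.0384 | 0.008–0.012 | 0.14–0.21 | 5.2–5.5% | 0.17–0.26 | 5.3–5.8% |

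*Stimulation-by-strategy interaction.* If the deficit is the same on both lists, the shift is zero. If it differs by 0.05–0.10 and all 3 left the sham arm, the shift is 3/28 × 0.05–0.10 = 0.005–0.011. Averaging over the two intervals, each list mean has variance 0.04 × (1+0.5)/2 = 0.03 and the covariance between lists is 0.5 × 0.04 = 0.02. The SD of the contrast is √[2 × (0.03 − 0.02)] = 0.141, the SE is 0.0393, and the shift is 0.14–0.27 SE (type I error 5.2–5.9%).

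**Would a different analysis help?**

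The 52 are those who entered learning and testing. Any loss from 55 to 52 after allocation therefore happened before there was recall data, and no model recovers those patients. Among the 52, testing is described as complete. A linear mixed model for recall with the same effects and matching patient-level random terms would then normally give the same F tests as the ANOVA. Setting hypothetical patients 0.2–0.3 below their arm mean would only display the assumption.

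**The case for a change.** The strongest case for acting is that, within one clause, understanding is put as an ability and cooperation as an accomplished act. Eligibility criteria belong in the protocol, so a faulty one cannot be left to an SAP. The phrase final group hints at an earlier, larger group whose size by arm is never given. The remedy would be cheap, since the study is complete and allocation and attendance should be on record. The worst case is also not trivial: with all three losses in one arm, the error rate could reach about 11% on the four-cell scale.

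Some of this stands. The wording is poor, and a reader cannot confirm from the document how many were randomised to each arm. But numbers by arm with reasons for loss belong to the report of results, and their absence from a protocol is not an error in the plan. The analysis population and missing-data handling are commonly left to an SAP, which is not at hand here. The worst case stacks several unsupported steps: that three were lost after allocation, that all came from one arm because of the arm, and that they recalled 1 to 1.5 SD less than the rest (0.2–0.3 against SD 0.2).

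**Conclusion.** No change to the plan follows. Criterion (3) is loosely worded, and its sensible meaning, ability and willingness to do the tasks as judged at entry, is clear from its context. The document does not show that any randomised patient was excluded.

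If none was, the effect is zero. If three were lost and split 2/1, the effect on a 5% test is under one percentage point on either scale. Only a wholly one-sided loss would matter (6.5–11.3%), and nothing in the text points to it. The stimulation-by-strategy interaction, which bears most directly on the stated aim of combining stimulation with retrieval practice, is largely spared.

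These sizes rest on the assumed number of losses, deficit, SD and correlation; only 27, 25 and the 5% level come from the document. A record of a one-sided loss after allocation would alter the conclusion about the anodal–sham main effect. That would be a matter for reporting and interpreting the results, because no alternative model could restore the missing recall data.
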